#### 3 INTRODUCTION

This is a study of BMS-986253, a monoclonal antibody (mAb) against human interleukin-8 (IL-8), conducted in humans with advanced solid tumors. This study will evaluate the safety profile, tolerability, pharmacokinetics (PK), pharmacodynamics, and preliminary efficacy of BMS-986253 in combination with nivolumab (Parts 1A and 1B) or in combination with nivolumab and ipilimumab (Parts 1C and 2) in participants with advanced solid tumors.

Parts 1A and 1B will evaluate the safety, tolerability, PK, and pharmacodynamics of different doses of BMS-986253 in combination with nivolumab in participants with non-small cell lung cancer (NSCLC), melanoma, squamous cell carcinoma of the head and neck (SCCHN), urothelial cancer (UCC) and renal cell carcinoma (RCC), who have

Part 1C will evaluate the safety and tolerability of BMS-986253 in combination with nivolumab and ipilimumab in participants with melanoma, colorectal cancer (CRC), hepatocellular cancer (HCC), and UCC, who may have any serum IL-8 level. Part 2 is a randomized, double-blind evaluation to assess efficacy of BMS-986253 in combination with nivolumab and ipilimumab versus placebo plus nivolumab and ipilimumab in participants with unresectable or metastatic melanoma.

## 3.1 Study Rationale

Immuno-oncology (I-O) drugs, which harness the immune system to fight cancer, have emerged as a major advancement in cancer treatment. Current approaches include blocking immunosuppressive signals, such as programmed cell death 1 (PD-1) or cytotoxic T-lymphocyte-associated protein 4 (CTLA-4) with antagonistic antibodies and stimulating immunity with agonistic antibodies. Despite recent progress, in many cases resistance to the immunotherapy occurs due to the interplay of various mechanisms of immune suppression. Thus, new combination strategies are needed to target these multiple mechanisms of immune suppression to overcome the resistance and to extend the breadth of current immune therapies.

There is growing evidence that IL-8 (also called CXCL8) plays an important role in immunosuppression. IL-8 belongs to the CXC chemokine subfamily that includes several molecules involved in the activation and chemoattraction of various leukocytes. IL-8 expression is highly regulated in healthy individuals with serum IL-8 concentrations at very low or undetectable levels

5,6 However, IL-8 serum concentrations are often elevated in cancer patients. IL-8 may be produced by a variety of cells, including cancer cells, leukocytes, endothelial cells, and fibroblasts. IL-8 binds to two receptors, CXCR1 and CXCR2, and promotes recruitment of myeloid derived suppressor cells (MDSCs) to the tumor microenvironment (TME), and suppress T-cell function.  IL-8 has also been shown to play a pro-tumoral role in the TME, and promote the epithelial mesenchymal transition (EMT), cancer stem cell (CSC) renewal,  and angiogenesis. 

In many types of advanced cancer, high levels of IL-8 correlate with worse prognosis as well as resistance to therapeutic approaches, including anti PD-1 and anti-CTLA-4 therapy.  One

Protocol Amendment No.: 07 Date: 17-May-2024

hypothesis that can explain this resistance is IL-8-dependent recruitment of immunosuppressive MDSC into the tumor.  Preliminary analysis of several clinical trials containing nivolumab-based therapy confirm recent observations made by other groups, that high levels of IL-8 are associated with resistance to anti-PD-L1-based therapy in advanced NSCLC, melanoma, and RCC (see Section 5.4.3).  Thus, blocking IL-8 with an antagonist antibody in combination with nivolumab or nivolumab plus ipilimumab represents an approach with the potential to extend I-O benefits to patients not adequately served by existing anti-PD-(L)1 therapies alone. Pharmacological inhibition of IL-8 is a rational approach to disrupt not only immunosuppression associated with MDSCs, but also pro-tumorigenic mechanisms of CSC maintenance, EMT, and angiogenesis.

# 3.2 Background

### 3.2.1 BMS-986253

BMS-986253 is a fully human-sequence IgG1k mAb directed against IL-8.

The antibody will thus antagonize the IL-8 mediated signals and may increase the anti-tumor response through distinct mechanisms of action:

- blocking the recruitment of immunosuppressive MDSC to the tumor
- disrupting angiogenesis
- inhibition of invasive EMT
- affecting the CSC phenotype

Furthermore, relieving the immunosuppression by reducing MDSCs in the tumor microenvironment has the potential to increase the activation of Effector CD8 T cells in synergy with PD-1 blockade by nivolumab. This study will, in part, evaluate this hypothesis in participants with NSCLC, melanoma, RCC, UCC, or SCCHN that progress on or after anti-PD-(L)1 therapy and which have a detectable level of IL-8 in the serum.

Previous data on treatment with BMS-986253 monotherapy in humans, demonstrated a safe and tolerable profile (see BMS-986253 Investigator's Brochure [IB]). The highest dose tested in humans was administered in the CA027001 Study, in which multiple ascending doses of BMS-986253 were found to be safe and well tolerated across the dose range of 4 to 32 mg/kg every 2 weeks (Q2W) in 15 participants with advanced tumors. This was equivalent to a 2560 mg flat dose for 80 kg body weight Q2W or a 5120 mg total accumulative dose Q4W. No serious adverse events (SAEs) were considered related to BMS-986253 monotherapy. There was no increase in the frequency of adverse events (AEs) with increased doses. There were no deaths or discontinuations due to AEs in this study. The maximum tolerated dose (MTD) was not reached.

The current study will evaluate the safety, tolerability, and preliminary efficacy of intravenous (IV) doses of BMS-986253, administered in combination with nivolumab or in combination with nivolumab and ipilimumab in participants with advanced solid tumors, and is expected to

Protocol Amendment No.: 07

determine the recommended Phase 2 dose(s) (RP2D) of the combination to be used in future studies.

It is anticipated that anti-IL-8 mAb (BMS-986253) administered in combination with anti-PD-1 mAb (nivolumab) or in combination with nivolumab and anti-CTLA-4 mAb (ipilimumab), will demonstrate adequate safety and tolerability, as well as a favorable risk/benefit profile to support further clinical testing.

The scientific rationale for the study design is discussed in greater detail in Section 5.3. Additional details such as BMS-986253 Nonclinical/Clinical Pharmacology, Nonclinical/Clinical PK/pharmacodynamics, Nonclinical Toxicology and clinical safety are summarized in the BMS-986253 IB.

#### 3.2.2 Nivolumab

Nivolumab is a fully human, IgG4 (kappa) isotype mAb that binds to PD-1 with nanomolar affinity (dissociation constant, 3.06 nM) and a high degree of specificity. Nivolumab blocks binding of PD-1 to its ligands programmed death ligand 1 (PD-L1) and programmed death ligand 2 (PD-L2). Nonclinical in vitro testing of nivolumab demonstrated that binding to PD-1 results in enhanced T-cell proliferation and release of interferon gamma in vitro in mixed lymphocyte reaction and cytomegalovirus assays.

The nonclinical safety of nivolumab was evaluated in a comprehensive toxicology program in mice and monkeys and was submitted as part of Biologics License Application 125554. Details of the in vitro and in vivo nonclinical pharmacology studies conducted to support the development of nivolumab can be found in Section 4.1 of the nivolumab IB.

While nivolumab was well tolerated in cynomolgus monkeys, there is a potential for enhanced toxicity when combined with other immunostimulatory agents. However, nonclinical studies with nivolumab did not predict clinically relevant adverse effects (eg, no evidence of immune-mediated adverse effects was observed in nonclinical toxicology studies with nivolumab). Therefore, combination nonclinical toxicology studies with BMS-986253 and nivolumab have not been conducted and are not required by the International Conference on Harmonisation S9 Note for Guidance on Nonclinical Evaluation for Anticancer Pharmaceuticals. The safety of the combination will be carefully monitored in the planned clinical trial.

The overall safety experience with nivolumab, as either monotherapy or in combination with other therapeutics, is based on experience in approximately 26,400 subjects (see nivolumab IB). Nivolumab has been approved by the United States (US) Food and Drug Administration (FDA) for various indications, including unresectable or metastatic melanoma (as a single agent and in combination with ipilimumab), metastatic NSCLC (as a single agent and in combination with ipilimumab), advanced RCC (as a single agent and in combination with ipilimumab), recurrent or metastatic squamous cell carcinoma of the head and neck with disease progression on or after a platinum-based therapy, advanced or metastatic urothelial carcinoma with disease progression on or after a platinum-based therapy, and MSI-H CRC (as a single agent or in combination with ipilimumab).

Protocol Amendment No.: 07

Date: 17-May-2024 62

For nivolumab monotherapy, the safety profile is similar across tumor types. The only exception is pulmonary inflammation AEs, which may be numerically greater in participants with NSCLC. In participants with NSCLC, it can be difficult to distinguish between nivolumab-related and unrelated causes of pulmonary symptoms and radiographic changes. There is no relationship between the incidence, severity, or causality of AEs and the nivolumab dose level. The safety of nivolumab in combination with other therapeutics such as ipilimumab, cytotoxic chemotherapy, anti-angiogenics, and targeted therapies is being explored in several ongoing clinical trials. The safety profile of nivolumab combination therapy varies with the agent combined with nivolumab, but is generally consistent with the safety profiles observed with either agent alone and, in some cases, both frequency and severity of AEs were greater than that observed with either agent alone. Additional details on the safety profile of nivolumab, including results from other clinical studies, are summarized in the nivolumab IB.

## 3.2.3 Ipilimumab

Ipilimumab is a fully human IgG1 (kappa) monoclonal antibody that binds to human cytotoxic T-lymphocyte antigen 4 (CTLA-4) with nanomolar affinity (dissociation constant 5.25 nM) and a high degree of specificity. CTLA-4 is expressed on a subset of activated T-cells on which it acts as a negative regulator of T-cell activity. Ipilimumab is a mAb that binds to CTLA-4 and blocks the interaction of CTLA-4 with its ligands, CD80/CD86. Blockade of CTLA-4 has been shown to augment T-cell activation and proliferation, including the activation and proliferation of tumor infiltrating T-effector cells. Inhibition of CTLA-4 signaling can also reduce Treg function, which may contribute to a general increase in T-cell responsiveness, including the anti-tumor response.

The overall safety experience of ipilimumab as either monotherapy or in combination with other therapeutics is based on experience in over 30,000 subjects. Additional details on the safety profile of ipilimumab, including results from other clinical studies, are summarized in the ipilimumab IB.

Ipilimumab has been approved by the US FDA for the treatment of several cancers, including unresectable or metastatic melanoma (single agent or combined with nivolumab), intermediate- or poor-risk RCC (in combination with nivolumab), MSI-H CRC that has progressed after chemotherapy (in combination with nivolumab), HCC that has previously been treated with sorafenib (in combination with nivolumab), and first-line NSCLC with PD-L1  $\geq$  1% (in combination with nivolumab).

### 3.2.4 Nivolumab plus Ipilimumab

The combination of nivolumab and ipilimumab has been approved by the US FDA for the treatment of patients across a variety of cancers, including melanoma, intermediate-/poor-risk-RCC, NSCLC, MSI-H CRC, and HCC (as indicated in Section 3.2.3). The safety profile of nivolumab plus ipilimumab is characterized by immune-related toxicities, such as diarrhea, rash, pneumonitis, liver toxicity, and endocrinopathies. The frequencies and intensities of these events in the combination are variable and depend on the specific doses and schedule used. Additional details on the safety profile on the combination of nivolumab and ipilimumab, are summarized in the nivolumab IB.

Protocol Amendment No.: 07 Date: 17-May-2024 Clinical Protocol CA027002 BMS-986253 Anti-IL-8

#### 3.3 Benefit/Risk Assessment

Patients who have advanced solid tumors including metastatic/unresectable melanoma, NSCLC, SCCHN, RCC, UCC, HCC, or CRC, that progress after at least 1 line of standard systemic therapy have a poor prognosis and no curative options.

The safety of BMS-986253 as monotherapy has been established in earlier studies in healthy volunteers, participants with inflammatory skin disease (Palmoplantar Pustulosis), and in participants with advanced malignancies. BMS-986253 monotherapy has been administered to participants with advanced malignancies

and was demonstrated to be safe and tolerable.

The safety profile of nivolumab monotherapy is well defined and is based on experience with greater than 15,000 participants evaluated in clinical trials. The frequency and types of immune-mediated adverse reactions (IMARs) are similar across multiple types of tumors and are described in the Reference Safety Information (RSI) in the current nivolumab IB. Management algorithms for nivolumab-induced AEs involving gastrointestinal, renal, pulmonary, hepatic, endocrinopathy, skin, and neurologic systems are included in the protocol (Appendix 5).

The safety profile of ipilimumab monotherapy is well defined and is based on experience with greater than 7,300 participants evaluated in clinical trials. The frequency and types of IMARs are similar across multiple types of tumors and are described in the RSI in the current ipilimumab IB. Management algorithms for ipilimumab-induced AEs involving myocarditis, gastrointestinal, renal, pulmonary, hepatic, endocrinopathy, skin, and neurologic systems are included in the protocol (Appendix 6).

In combination with nivolumab, the risk that BMS-986253 may potentiate immune-mediated adverse reactions should be low as blocking IL-8 does not directly activate T-cells. Blocking IL-8 may, in fact, reduce the inflammatory process by reducing the neutrophil recruitment in the

Protocol Amendment No.: 07

damaged tissue. Available safety data from trials using I-O combination strategies with nivolumab have shown that the safety profile varies depending on the agent being combined with nivolumab, but is generally consistent with the safety profiles observed with either agent alone and, in some cases, both the frequency and severity of AEs were greater than that observed with either agent alone. The safety of the combination of BMS-986253 with nivolumab will be carefully monitored in the study.

Overall, participants experienced Grade  $\geq$  3 related AEs, and participants discontinued study treatment because of AEs related to the study drugs (less than or similar to that expected with nivolumab monotherapy in an I-O naïve population). There were no deaths related to the study drugs, and there were no dose-dependent AEs identified. Based on these data, an increase in IMARs with the combination of BMS-986253 and nivolumab compared with nivolumab monotherapy is not expected.

The triplet combination of BMS-986253, nivolumab, and ipilimumab has not been previously evaluated. However, based on the safety data generated on the combination of BMS-986253 and nivolumab, and the combination of nivolumab and ipilimumab, the triplet combination is expected to have a tolerable safety profile. For similar reasons, as stated in the previous paragraph (mainly that blocking IL-8 may reduce the inflammatory process and safety data generated on the combination of BMS-986253 and nivolumab), BMS-986253 is not expected to increase the rate of IMARs observed with the combination of nivolumab and ipilimumab.

Continuous safety assessments will be utilized by the investigators and Bristol Myers Squibb (BMS) to determine whether dose modification, additional safety measures, or termination of the study is required at any time. In addition, AEs and SAEs will be reviewed on an ongoing basis by the BMS Medical Monitor and Global Pharmacovigilance and Epidemiology representatives to monitor for any safety signals or trends. Additionally, in Part 2 of the study, an independent safety or Data Monitoring Committee (DMC) will be used

As BMS-986253 is an experimental agent, it is possible that unforeseen, unknown, or unanticipated reactions may occur. The protocol was developed while carefully balancing risks and benefits of treatment of a novel treatment in this patient population.

Protocol Amendment No.: 07

Approved v 8.0

930120018 9.0

# 3.3.1 Safety Monitoring on Study Treatment

Frequent safety assessments will be carried out by the Sponsor/BMS Medical Monitor (or designee) and investigators throughout the study to determine whether dose modification, additional safety measures, or termination of the study treatment combination arm is required at any time. In addition, AEs and SAEs will be reviewed regularly by the BMS Medical Monitor (or designee) and the Pharmacovigilance group to look for trends and potential safety signals. Treatment of AEs will follow institutional guidelines and recommended management algorithms, as listed in the IBs and prescribing information, as applicable, for each combination agent, and provided as appendices to this protocol. Specific algorithms for the management of immune-related adverse events (irAEs) are provided in Appendix 6 and are applicable to irAEs for all I-O study treatment combinations.

The global coronavirus disease 2019 (COVID-19) pandemic has been identified as a potential risk to clinical trial participants in general. Whether BMS-986253 in combination with nivolumab or in combination with nivolumab and ipilimumab administration increases the risk for contracting severe acute respiratory syndrome coronavirus 2 (SARS-CoV-2) infection or increases the severity or duration of symptoms is currently unknown. This unknown risk must be considered when enrolling a participant.

No additional safety monitoring or routine screening tests will be required due to the SARS-CoV-2 pandemic. Participants with a recent or acute infection will be excluded or delay start of treatment as defined in Section 6.2. If a participant has a confirmed SARS-CoV-2 infection while on study treatment, dose delay or interruption of study treatment is required as described in Section 7.6.3.

The study has been designed with study visits that allow for close monitoring of participants' safety throughout the clinical trial (Section 9.1), and participants are encouraged to contact the investigator if an intercurrent illness develops between study visits. Testing for COVID-19 to inform decisions about clinical care during the study should follow local standard practice.

Non-live COVID-19 vaccination is considered a simple concomitant medication within the study. However, the efficacy and safety of non-live vaccines (including non-live COVID-19 vaccines) in participants receiving BMS-986253 in combination with nivolumab or in combination with nivolumab and ipilimumab is unknown.

Additionally, in Part 2 of this study, an independent DMC will provide oversight. The DMC will act in an advisory capacity to BMS and will monitor participant safety and evaluate the available efficacy data for the study. They will advise the Sponsor regarding actions the committee deems necessary for the continuing protection of participants enrolled in the study and those yet to be recruited to the trial as well as for the continuing validity and scientific merit of the study results. The DMC is charged with assessing such actions in light of an acceptable benefit-risk profile for BMS-986253.

The oncology therapeutic area of BMS has primary responsibility for design and conduct of the study.

Protocol Amendment No.: 07

# 4 OBJECTIVES AND ENDPOINTS

Table 4-1: Objectives and Endpoints - Part 1

Objectives	Endpoints
Primary	
To characterize safety, tolerability, and DLTs, and to determine the RP2D of BMS-986253 administered in combination with nivolumab, or in combination with nivolumab and ipilimumab in participants with advanced solid tumors.	Incidence of AEs, SAEs, AEs meeting protocol- defined DLT criteria, and AEs leading to discontinuation, death, and laboratory abnormalities.
Secondary	

 
To evaluate the preliminary efficacy of BMS-986253 in combination with nivolumab in participants with advanced solid tumors using RECIST v1.1.
 
To characterize the PK and immunogenicity of BMS-986253 when administered in combination with nivolumab, or in combination with nivolumab and ipilimumab in participants with advanced solid tumors.
 
To assess serum IL-8 levels at baseline (ie, screening) and changes in IL-8 levels on treatment.
 
	
 
ORR and DOR per RECIST v1.1 per investigator.
 
Summary measures of PK parameters and incidence of ADA to BMS-986253.
 
Summary measures of IL-8 and change (or percent change) from baseline in IL-8 on treatment.
 

Abbreviations: ADA, anti-drug antibody; AE, adverse event; DLT, dose-limiting toxicity; DOR, duration of response; EOT, end of treatment; ORR, objective response rate; PK, pharmacokinetic(s);

Protocol Amendment No.: 07

RECIST, Response

Evaluation Criteria in Solid Tumors; RP2D, recommended Phase 2 dose; SAE, serious adverse event.

[figure not shown]
Table 4-2: Objectives and Endpoints - Part 2

	Objectives	Endpoints
Pri	imary	
•	To compare the ORR of BMS-986253 plus nivolumab plus ipilimumab with placebo plus nivolumab and ipilimumab using RECIST v1.1.	ORR based on BICR assessments per RECIST v1.1 in all randomized participants.
Sec	condary	
•	To estimate PFS of BMS-986253 plus nivolumab plus ipilimumab and placebo plus nivolumab and ipilimumab in participants with advanced melanoma using RECIST v1.1 (regardless of baseline serum IL-8 levels).	mPFS and PFS hazard ratio based on BICI assessments per RECIST v1.1.
•	To compare the safety of BMS-986253 plus nivolumab plus ipilimumab with placebo plus nivolumab plus ipilimumab in participants with advanced melanoma.	discontinuation, death, and laborator

Protocol Amendment No.: 07

Date: 17-May-2024 68

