# 2 SCHEDULE OF ACTIVITIES

Table 2-1: Prescreening Procedural Outline (applicable for Part 1 only)

Procedure	Prescreening Visit	Notes
Eligibility Assessments		
		Participants must sign the Pre-Screen Informed Consent prior to testing the screening serum IL-8 level. The pre-screen testing for serum IL-8 will occur before the 28-day screening window. Participants may not receive any systemic therapy after screening serum IL-8 is drawn.
Prescreen Informed Consent for Serum IL-8	X	Depending on availability of cohorts at the time of enrollment, serum IL-8 results may determine eligibility and cohort assignment.
		For participants with CRC and HCC: results of screening IL-8 are not required prior to signing the Main Informed Consent.
		For participants with melanoma or UCC only being considered for Part 1C (for example, if Part 1B is not actively enrolling participants), results of screening IL-8 are NOT required prior to signing the Main Informed Consent.
IRT Assignment	X	To obtain participant identification number. This must be done prior to testing screening serum IL-8.
Laboratory Test for Serum IL-8	X	
Adverse Event Reporting		
Monitor for Serious Adverse Events	X	All SAEs related to the blood draw must be collected from the date of participant's written consent (Pre-screen ICF) and followed until resolution or stabilization of the SAE.

Abbreviations: CRC, colorectal cancer; HCC, hepatocellular cancer; IL-8, interleukin-8; IRT, Interactive Response Technologies; SAE, serious adverse event.

Protocol Amendment No.: 07

Date: 17-May-2024

Approved v8.0 930120018 9.0

30

 Table 2-2:
 Screening Procedural Outline (All Study Phases)

Procedure	Screening Visit Day -28 to Day -1	Notes
Eligibility Assessments		
Main Informed Consent	X	For participants in Part 1: eligible participants (as determined by serum IL-8 prescreen results and cohort availability) must sign the main informed consent within 1 week of serum IL-8 positive result by the central laboratory.  For Part 1 participants with CRC and HCC: results of screening IL-8 are not required prior to signing the Main Informed Consent. All CRC and HCC participants will be assigned to Part 1C, and may enroll only when Part 1C is open.
ECOG Performance Status	X	Appendix 5
Inclusion/Exclusion Criteria	X	

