# 5.1.1 Pre-Screening Period (Applicable for Part 1 Only)

Participants will provide consent for pre-screening to obtain a serum IL-8 level; further screening procedures will not be completed until the IL-8 level is resulted (except for participants with HCC and CRC). Depending on availability of cohorts at the time of enrollment, serum IL-8 results may determine eligibility and cohort assignment.

- Enrollment into Part 1B requires
- Enrollment into Part 1C does NOT require a minimum serum IL-8 level.
- For participants with HCC and CRC: results of screening IL-8 are NOT required prior to signing the Main Informed Consent, since all HCC and CRC participants will be assigned to Part 1C (Part 1C does not require a minimum serum IL-8 level). Participants with HCC and CRC may enroll only when Part 1C is open.
- For participants with melanoma or UCC only being considered for Part 1C (for example, if Part 1B is not actively enrolling participants), results of screening IL-8 are NOT required prior to signing the Main Informed Consent.

If the participant meets pre-screening criterion for study entry, the Main Informed Consent must be signed within 1 week of serum IL-8 positive result by the central laboratory. Participants will be enrolled using Interactive Response Technology (IRT) during Pre-Screening and will be assigned a designated subject identification number.

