## 5.1.2 Screening Period

The screening period will be up to 28 days and begins by establishing the participant's initial eligibility and signing of the informed consent form (ICF). In order to establish eligibility for this study, participants will undergo baseline physical examinations, vital signs and oxygen saturation measurements, 12-lead electrocardiogram (ECG), and clinical laboratory evaluations.

If a participant exceeds the 28-day screening period (eg, waiting for a laboratory value), the participant must be reconsented, but does not require a new participant identification number. The fewest number of procedures from the initial screening should be repeated to qualify the participant, while maintaining participant safety and eligibility. Repeat serum IL-8 testing will not be required if the previous sample was obtained within 42 days of study treatment initiation.

Assignment to a Study Part 1 (1A, 1B, or 1C) must be designated in the IRT system prior to the participant's assignment to a dosing regimen. In Part 2, all participants will be randomly assigned to Arm 2A (BMS-986253 + nivolumab + ipilimumab) or 2B (placebo + nivolumab + ipilimumab). Prior to randomization in Part 2, screening laboratory test results for serum IL-8 and LDH must be received, and must be entered in the electronic case report form (eCRF). Part 2 of the study is double-blind; the participant, Sponsor, and site staff (except as indicated in Section 7.5) will not be aware of treatment/cohort assignment, as described in Section 7.4.

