# 5.4.1 Rationale for Targeting IL-8 in Cancer

IL-8 (CXCL8) is a chemokine whose main physiologic function is the attraction of a polymorphonuclear inflammatory leukocyte infiltrate acting on CXCR1/2. Recently, it has been found that tumors frequently produce IL-8, which exerts different pro-tumoral functions, including

Protocol Amendment No.: 07

angiogenesis, provide growth factors and survival signaling for CSCs as well as the attraction of immunosuppressive myeloid cells endowed with the ability to dampen anti-tumor immunity. In the tumor, IL-8 is mainly produced by cancer cells themselves. IL-8 serum concentration has been shown to correlate with cumulative tumor size, stage, and prognosis in numerous cancer types.  Because of a short concentrations closely follow in time the changes occurring in IL-8-producing cells. Recent data strongly support a correlation between serum IL-8 levels and tumor burden as well as clinical stage in patients with melanoma, RCC, NSCLC, and HCC.  In fact, patients with higher serum IL-8 levels had worse overall survival (OS). Because of the roles that IL-8 plays in favoring tumor progression through several mechanism such as modulating chemotaxis, resistance to therapy, angiogenesis, and metastasis, therapeutic strategies aiming to interfere with IL-8 has the potential to alleviate these functions, thereby diminishing the risk of (further) metastatic spread and recurrent disease in these patients. Anti-IL-8 neutralizing antibody (HuMax-IL-8) was shown to decrease IL-8-induced neutrophil activation and migration in vitro resulting in beneficial anti-inflammatory responses in patients with palmoplantar pustulosis which also provided support to test this antibody in cancer patients.

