# 3) Physical and Laboratory Test Findings

Participants must have:

- a) Baseline (only required for Part 1A and Part 1B)
- b) Adequate hematologic function as defined by the following:
  - i) Neutrophils  $\geq 1,500 \mu L$
  - ii) Platelets  $\geq 80 \times 10^3/\mu L$  (transfusion to achieve this level is not permitted within 2 weeks of first study treatment administration)
  - iii) Hemoglobin  $\geq 8$  g/dL (transfusion to achieve this level is not permitted within 2 weeks of first study treatment administration)
- c) Adequate hepatic function
  - i) Alanine aminotransferase (ALT) and aspartate aminotransferase (AST)  $\leq$  3× upper limit of normal (ULN)
  - ii) Total bilirubin  $\leq 1.5 \times$  ULN (except participants with Gilbert's Syndrome who must have normal direct bilirubin)

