# 10.3.5 Biomarker Analyses

Endpoint	Statistical Analysis Methods
Summary measures of absolute values of serum IL-8, and change (or percent change) from baseline in serum IL-8	Summary statistics by planned study day and cohort; Plots of the time course of biomarkers, geometric mean of the ratio of post-baseline IL-8 and corresponding CI.

[figure not shown]
Abbreviations: CI, confidence interval; IL-8, interleukin-8.

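### In Parts 1A and 1B the IL-8 value used for entry is also the baseline for change, so regression to the mean overstates the absolute on-treatment fall

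*Combined protocol and SAP*

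**What the plan says.** Section 4, Table 4-1 states the objective as "To assess serum IL-8 levels at baseline (ie, screening) and changes in IL-8 levels on treatment". The matching endpoint is "Summary measures of IL-8 and change (or percent change) from baseline in IL-8 on treatment", and Section 10.3.5 analyses "change (or percent change) from baseline in serum IL-8" with a geometric mean ratio and confidence interval by study day and cohort.

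Four further places fix which sample this is in Part 1:

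- Table 2-1 uses the term screening serum IL-8 for the pre-screen draw and places it early: "The pre-screen testing for serum IL-8 will occur before the 28-day screening window".
- Table 2-2 lists an IL-8 test at the main screening visit for Part 2 only.
- Section 5.1.2, dealing with screening that overruns 28 days, adds: "Repeat serum IL-8 testing will not be required if the previous sample was obtained within 42 days of study treatment initiation".
- Section 6.1, criterion 3a, sets a baseline IL-8 requirement that is "only required for Part 1A and Part 1B". For 1C, Section 5.1.1 says "Enrollment into Part 1C does NOT require a minimum serum IL-8 level".

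The numeric threshold is not visible. Its type is partly visible: Section 3.2.1 speaks of detectable serum IL-8, and Section 9.8.1 bases inclusion on a certified analytical cut-off, leaving high and low categories to post-hoc allocation.

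**The concern.** A participant who clears a floor on a single draw does so partly through a true level above it and partly through a chance high reading. On the next draw the chance part does not repeat, so the group mean drops with no treatment at all. When the selecting draw is also the denominator, that drop is counted as on-treatment suppression. Nothing visible in Section 10.3.5 allows for it.

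The stake is the absolute suppression figure in 1A and 1B. This is a secondary pharmacodynamic endpoint, and Section 5.5.2 names serum IL-8 data among the grounds for the Q2W option and for the maximum administered dose. The gap between the pre-screen draw and first dose adds a second source of error. Section 5.4.1 says that serum "concentrations closely follow in time the changes occurring in IL-8-producing cells", so an old sample may no longer describe the participant at first dose.

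**Working it through.** The plan gives no variance, expected change or power for IL-8, so there is no figure to reproduce.

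**Inputs.** From the protocol: baseline is the screening value, the screening value is the entry draw in 1A/1B, and change is summarised as a ratio. Assumed, because the protocol does not give them:

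- log-normal IL-8 with total log-SD σ of 0.7 to 1.0;
- correlation r between repeat draws of 0.5 to 0.8;
- share of candidates excluded by the cut-off, q, of 5% to 10%, as a detectability-type floor might do.

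**Formula.** With no drug effect, the expected ratio of a later draw to the screening draw among those admitted is

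ratio = exp[−(1 − r) × σ × λ], with λ = φ(z_q)/(1 − q),

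where z_q is the standard normal quantile at q and φ is the normal density.

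**Results.** The mild case is r = 0.8, σ = 0.7, so (1 − r)σ = 0.14. The strong case is r = 0.5, σ = 1.0, so (1 − r)σ = 0.50.

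| Excluded | λ | Mild case | Strong case |
|---|---|---|---|
| 5% | 0.1086 | exp(−0.0152) = 0.985, fall 1.5% | exp(−0.0543) = 0.947, fall 5.3% |
| 10% | 0.1950 | exp(−0.0273) = 0.973, fall 2.7% | exp(−0.0975) = 0.907, fall 9.3% |

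**On top of a real effect.** The artefact multiplies the ratio. With 10% excluded:

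- a true 90% reduction reads as 1 − 0.1 × 0.973 = 90.3% to 1 − 0.1 × 0.907 = 90.9%;
- a true 50% reduction reads as 1 − 0.5 × 0.973 = 51.3% to 1 − 0.5 × 0.907 = 54.6%.

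The distortion is therefore small where suppression is deep and more visible where it is partial.

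**Does another baseline remove it?** In a simulation of 2,000,000 draws (σ = 0.8, 10% excluded, no drug effect), the ratio to the screening value was 0.924 at r = 0.5 and 0.954 at r = 0.7. The ratio to a separate pre-dose draw was 1.00 in both.

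**Does it disturb dose contrasts within 1B?** Two arms under one entry rule (σ = 0.8, r = 0.7, 25% excluded) were given true ratios of 0.50 and 0.20. They showed 0.451 and 0.181, but the ratio between them was 0.400 against a true 0.40. The artefact cancels.

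**The case against.** The strongest reply is that the effect may be trivial. The visible text points to a detectability or analytical floor, and if that excludes few candidates the bias is a few percent. This stands, and it is why the size is given as a conditional range. A reader might take a much larger figure: the same formula gives 16% to 47% if the cut-off sits at the upper quartile. No passage supports a cut-off there.

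The net direction is also open. Section 5.4.1 ties IL-8 to tumor burden, so tumor growth between the pre-screen draw and first dose would raise IL-8 and work against regression to the mean. That IL-8 tracks its producing cells does not by itself show random within-person variation, so r remains an assumption. Both points stand. They leave the absolute change harder to interpret and do not rescue the screening baseline.

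A reader might infer that the artefact makes 1B and 1C non-comparable. The protocol plans no such IL-8 contrast, and the two parts already differ in ipilimumab and in tumor types (Section 5.1). Nor is 1C clearly free of bias. Section 5.1.1 lets IL-8 influence cohort assignment and Section 7.4 has 1B and 1C enrolling together, so low-IL-8 candidates may be routed to 1C and show an apparent rise.

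A reader might also infer that the dose choice is undermined. Section 5.5.2 rests it on the totality of Part 1 data, and the IL-8 findings cited there include dose and frequency dependence. Common entry rules and randomisation largely protect that pattern in 1B1 to 1B3. For the sequential cohorts 1B4 to 1B6, protection depends on similar case mix.

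Finally, the words naming screening stand in the objective, while the endpoint and Section 10.3.5 say only baseline, and the sampling schedule in Section 9.8 is not visible. A Day 1 pre-dose sample may well exist. Even so, the only visible definition of baseline is the screening value.

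**Conclusion.** The point holds for the absolute IL-8 change in Parts 1A and 1B. On the visible text, the entry value is also the denominator, and regression to the mean inflates the reported fall. Under the stated assumptions the inflation with no drug effect is about 1.5% to 9% if 5% to 10% of candidates are excluded. It is larger only if many more are excluded, and it shrinks as repeat draws agree more closely. For deep suppression the reported percentage moves by less than one point. The endpoint is descriptive and secondary in a part not powered for it, so the consequence is modest, but the bias is avoidable. The documents do not support extending it to a 1B-versus-1C claim or to the dose ranking among 1B1 to 1B3.

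**What to change.** In Tables 1 and 4-1 and in Section 10.3.5, define IL-8 baseline for change, percent change and the geometric mean ratio as the last pre-dose sample not used for eligibility, normally Cycle 1 Day 1 pre-dose. Where no biomarker aliquot exists, Section 9.5 already allows pharmacokinetic or immunogenicity serum from the same time point to be used if required. Keep the pre-screen value for eligibility and for describing screening levels, and report change from it only as a sensitivity analysis. For a participant with no such pre-dose sample, report change from screening separately, with the selection caveat.

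Section 10.3 has the SAP finalised before database lock, which is the natural place to carry the definition through. The cost is wording and possibly assay of some stored serum. Reported suppression will look slightly less favourable. Some Day 1 values may fall below quantitation, so the SAP needs a stated rule for handling them.
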